7.5 Safety Assessments

7.5.1 Adverse Events

Subjects will be monitored for AEs from administration of the first dose (insertion of IVR or first oral dose, as applicable) of study drug through the follow-up phone call. Refer to Section 8 for additional details.

7.5.2 Laboratory Tests

A certified laboratory will be utilized to process and provide results for the clinical laboratory tests listed in Table 7.1. The baseline laboratory test results for clinical assessment for a particular test will be defined as the last measurement prior to the first dose of study drug.

Subjects will fast a minimum of 8 hours prior to clinical laboratory sample collection at screening.

During screening, if a subject has an out-of-range value for a clinical laboratory parameter that the investigator believes is not clinically significant or the investigator does not believe is correct (e.g., lab or specimen processing error), but the investigator wants to confirm with a repeat laboratory test, a single repeat is allowed to confirm the initial result.

Additional safety laboratory tests may be conducted as needed by the investigator to evaluate subject safety.

CONFIDENTIAL

Table 7.1 Clinical Laboratory Tests

| Hematology | Chemistry | Urine Dipstick |
|--|----------------------------|---|
| Hematocrit | Albumin | Specific gravity |
| Hemoglobin | Alkaline phosphatase | Ketones |
| Red blood cell count | Alanine aminotransferase | pH |
| White blood cell count | Aspartate aminotransferase | Protein |
| Neutrophils (absolute) | Gamma glutamyl transferase | Blood |
| Lymphocytes (absolute) | Direct bilirubin | Glucose |
| Monocytes (absolute) | Total bilirubin | Leukocyte esterase |
| Basophils (absolute) | Lactate dehydrogenase | Microscopic analysis (performed if blood, leukocytes, or protein are present) |
| Eosinophils (absolute) | Total protein | |
| Platelet count (estimate not acceptable) | Blood urea nitrogen | |
| | Creatinine | |
| | Calcium | |
| | Phosphate | |
| | Sodium | |
| | Potassium | |
| | Carbon dioxide | |
| | Chloride | |
| | Glucose ^a | |
| | Total cholesterol | |
| | Triglycerides ^a | |

a. Fasting

For any laboratory test value outside the reference range that the investigator considers clinically significant during the on-study period (i.e., following dose administration), the investigator will:

- Repeat the test to verify the out-of-range value and clinical significance.
- Follow the out-of-range value until the value returns to normal or baseline, or until the value is deemed stable and not clinically significant by the investigator.
- Record as an AE any laboratory test value that is confirmed by repeat and the investigator considers clinically significant, requires a subject to be discontinued from the study, requires a subject to receive treatment, or requires a change or discontinuation of the study drug (if applicable).

CONFIDENTIAL

7.5.3 Other Tests

The following tests will be performed:

- Urine drugs of abuse (at a minimum, cocaine, tetrahydrocannabinol, amphetamines, opiates, and phencyclidine), and alcohol screens
 - During the screening period, urine drugs of abuse, and alcohol screens may not be repeated for eligibility
- Serology tests (i.e., HIV-1 and HIV-2 antibodies, hepatitis B surface antigen, and HCV antibody, and any confirmatory tests performed at the discretion of the investigator)
- FSH (screening only; as needed to confirm postmenopausal status)
- Transvaginal ultrasound
- Cervical screening test (if needed)
- Pelvic examination with speculum and vaginal visual examination
- Vaginal cytology and pH
- Endometrial biopsy

7.5.4 Usability and Tolerability Questionnaire

A Usability and Tolerability questionnaire will be administered to all IVR subjects at the end of the study.

7.5.5 Vital Signs

Vital signs assessments will include oral temperature (C°), respiratory rate (breaths per minute), systolic and diastolic blood pressure (mmHg) and pulse rate (bpm). Blood pressure and pulse rate will be measured after the subject has been resting quietly in a supine position or in the most recumbent position possible for at least 5 minutes. Any clinically significant abnormal vital sign assessment requires at least one repeat measurement.

Vital signs abnormalities that are considered clinically significant initially and on confirmation, require a subject to be discontinued from the study, require a subject to receive treatment, or require a change or discontinuation from the study drug (if applicable) will be recorded as AEs.

7.5.6 Physical Examination

Comprehensive physical examinations (excluding rectal and breast examinations [unless indicated]) will be performed, and abnormal findings will be documented in the subject's eCRF. Pelvic speculum and visual examinations will be conducted to identify vaginal irritation or abnormalities at baseline (screening) and for IVR treatment arm subjects on Day 30.

CONFIDENTIAL

An abnormal physical examination finding that is considered clinically significant and requires the subject to be discontinued from the study, requires the subject to receive treatment, or requires a change or discontinuation of the study drug (if applicable) will be recorded as an AE.

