- b. Randomization will occur after screening procedures are completed and eligibility is verified.
- c. Complete physical examination at Screening and Day 30 visit. Symptom-directed examination at all other visits for subjects exhibiting or reporting symptoms since their last visit.
- d. The purpose of the pelvic speculum exam is to identify vaginal irritation or abnormalities at baseline so that AEs related to IVR can be associated with IVR and not baseline abnormalities.
- e. Serology tests include HIV-1 and HIV-2 antibodies, hepatitis B surface antigen, and HCV antibodies.
- f. Placement of IVR will be confirmed prior to first post-dose PK collection.
- g. The purpose of the call is to follow up on any ongoing or emergent AEs since discharge from the CRU after the subject's treatment has been completed (approximately 7 days after the last dose of study medication or removal of the IVR).

CONFIDENTIAL

Table 1.2 Schedule of Assessments and Procedures - Oral Treatment Arm

| Study Procedure | Screening | Pre- Treatment | | Treatment Phase | | | | | | | Follow-Up Phone Call |
|--|--------------|----------------|----------------|-----------------|-------|--------|--------|--------|-----------|---------|----------------------|
| | | Days -28 to -2 | Day -1 | Day 1 Predose | | | | | In-Clinic | | |
| Study Day | Days 1 and 2 | | | | Day 8 | Day 15 | Day 22 | Day 28 | Day 29 | Day 30 | |
| Informed consent ^a | X | | | | | | | | | | |
| Assign Subject ID | X | | | | | | | | | | |
| Eligibility assessment | X | | X | | | | | | | | |
| Randomization | | | X ^b | | | | | | | | |
| Admission to CRU | | X | | | | | | X | | | |
| Demographics | X | | | | | | | | | | |
| Medical and surgical history | X | X | | | | | | | | | |
| Physical examination ^c | X | X | | | | | | | | X | |
| Height (cm), weight (kg), and BMI | X | | | | | | | | | | |
| Cervical screening test (if needed) | X | | | | | | | | | | |
| Pelvic exam with speculum & vaginal visual exam ^d | X | | | | | | | | | | |
| Vaginal cytology and pH | X | | | | | | | | | X | |
| Endometrial biopsy | X | | | | | | | | | | |
| 12-lead ECG | X | X | | | | | | | | | |
| Vital signs (BP and PR), RR, oral temp | X | X | X | | X | X | X | | | X | |
| Hematology & blood chemistry | X | X | | | X | X | X | | | X (EOS) | |
| FSH | X | | | | | | | | | | |
| Serology tests ^e | X | | | | | | | | | | |

CONFIDENTIAL

Table 1.2 Schedule of Assessments and Procedures - Oral Treatment Arm

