Day 1 is defined as the first day of treatment, i.e., the day the IVR is self-inserted by the subject. The same IVR is to remain intravaginal for 28 days, with removal of IVR in the CRU on the morning of Day 29. For those randomized to the oral arm (Estrace/Prometrium), dosing will also begin on Day 1, concluding with a last dose on Day 29. Subjects in the oral arm will be directed to self-administer the medication in the morning with a meal and approximately 240 mL of water, starting on Day 2 through Day 27. Doses will be administered in the CRU each of the mornings of Day 1 and Days 28 and 29 with a moderate-fat breakfast.

Safety and tolerability assessments will include monitoring of adverse events and concomitant medications, clinical laboratory findings, physical examinations, vital signs, pelvic examinations, completion of a Usability and Tolerability questionnaire, and vaginal pH and cytology. Refer to the Schedule of Assessments for each treatment arm in Table 1.1 and [Table 1.2](#) for specific details.

IVR Treatment Groups:

- A single predose blood draw for estradiol, estrone, and progesterone will be obtained at screening and Day -1, and -1, -0.5, and 0 (immediately prior to insertion of IVR \pm 5 min) hours on Day 1. Plasma samples for estradiol, estrone, and progesterone will then be obtained at 0.5, 1, 2, 4, 8, 12, 24, and 48 hours following administration/insertion. Subjects will then be discharged from the CRU after safety assessments have been completed on Day 3.
- Subjects will return on the morning of Days 8, 11, 15, and 22 for a single blood draw as well as safety assessments.
- Subjects will return to the CRU on Day 28 for a PK blood draw, safety assessments, confirmation of IVR placement, and to begin confinement. On the morning of Day 29 a PK blood sample will be collected. The IVR will then be removed and PK samples will be collected 0.5, 1, 2, 4, 8, 12, and 24 hours post-removal.

Additional details of sampling and safety assessment procedures are presented in the Schedule of Assessments and Procedures - IVR Treatment Arm in Table 1.1.

Oral Treatment Group:

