8 ADVERSE EVENTS

An AE is defined as any untoward medical occurrence in a subject administered a pharmaceutical product during the course of a clinical investigation. An AE can therefore be any unfavorable and unintended sign, symptom, or disease temporally associated with the use of a study drug, whether or not thought to be related to the study drug.

Subjects will be monitored throughout the study for AEs, from IVR placement or first oral dose, as applicable, through the follow-up phone call. Adverse events that are identified at the last assessment visit (or the early termination visit) as specified in the protocol must be recorded on the AE eCRF with the status of the AE noted. All events that are ongoing at this time will be recorded as ongoing on the eCRF. All (both serious and nonserious) AEs must be followed until they are resolved or stabilized, or until reasonable attempts to determine resolution of the event are exhausted. The investigator should use his/her discretion in ordering additional tests as necessary to monitor the resolution of such events.

The procedures specified in Section 8.4 are to be followed for reporting SAEs.

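### Section 7.5.6's adverse event rule for examination findings is narrower than Sections 7.5.2, 7.5.5 and 8, so whether an untreated Day 30 ring finding enters the AE table depends on which section is followed

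*Combined protocol and SAP*

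**What the plan says.** Section 7.5.6 first describes the pelvic speculum and visual examinations, which take place "at baseline (screening) and for IVR treatment arm subjects on Day 30". It then gives the recording rule: "An abnormal physical examination finding that is considered clinically significant and requires the subject to be discontinued from the study", with the further alternatives "requires the subject to receive treatment, or requires a change or discontinuation of the study drug (if applicable) will be recorded as an AE".

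Other parts of the protocol bear on the same question:

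- **Ring removal (Section 4.1).** The ring stays in for 28 days, "with removal of IVR in the CRU on the morning of Day 29". The Day 30 examination therefore follows removal.
- **Purpose of the examination (footnote d to Table 1.1).** "The purpose of the pelvic speculum exam is to identify vaginal irritation or abnormalities at baseline so that AEs related to IVR can be associated". The footnote means attribution to the ring as opposed to an abnormality that was already present.
- **Laboratory values (Section 7.5.2).** "Record as an AE any laboratory test value that is confirmed by repeat and the investigator considers clinically significant, requires a subject to be discontinued", followed by treatment or a change of study drug as further alternatives.
- **Vital signs (Section 7.5.5).** The rule is built the same way: clinical significance that is confirmed is one item in a list of alternatives.
- **General definition (Section 8).** "An AE can therefore be any unfavorable and unintended sign, symptom, or disease temporally associated with the use of a study drug". No judgment of relatedness is needed. Collection runs to the follow-up phone call.
- **Grade 1 (Section 8.2.2).** Mild events include those that need no specific treatment.
- **Analysis (Sections 9.4.2 and 9.6).** Pelvic examination findings are a secondary endpoint of their own and are tabulated or summarized. Classification by severity and relationship is planned for treatment-emergent AEs.

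**The concern.** The protocol has three rules for turning an abnormal observation into an AE. The one for examinations is the only one that asks for a consequence on top of clinical significance. It sits in the section that describes the speculum examination, where local effects of the ring would be seen. Safety and tolerability is a secondary objective, and the product has not been given to humans before.

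What is at stake is the content of the treatment-emergent AE table. Under Section 8.2 the investigator assesses seriousness, intensity and relationship for each AE. A finding that is entered only as an examination result has no planned grade or causality assessment, and the analysis cannot supply one later. If Sections 7.5.6 and 8 give different answers for the same lesion, the count of local reactions reflects staff's choice of section as well as what happened to the subjects.

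**Working it through.** The protocol states no rate or formula for this rule, so there is no figure to reproduce. The check is one of logic.

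**Inputs.** For each finding let

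- CS = judged clinically significant
- D = requires discontinuation from the study
- T = requires treatment
- C = requires a change or stop of study drug

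**Rules.**

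- Section 7.5.6, natural reading: CS and (D or T or C)
- Section 7.5.6, alternative parsing: (CS and D) or T or C
- Sections 7.5.2 and 7.5.5, after confirmation: CS or D or T or C

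**Which consequences remain on Day 30?** For a subject who completes, the ring came out the day before, so C has nothing to act on. Day 30 is her last clinic visit and only a phone call about 7 days after removal follows, so D is empty in practice. Setting D = C = 0 reduces the three rules to *CS and T*, *T*, and *CS or T*.

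| CS | T | 7.5.6, natural reading | 7.5.6, alternative parsing | 7.5.2 / 7.5.5 style |
|---|---|---|---|---|
| no | no | not met | not met | not met |
| no | yes | not met | met | met |
| yes | no | **not met** | **not met** | **met** |
| yes | yes | met | met | met |

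The third row is the gap. A clinically significant finding that is left untreated, for example because it is expected to heal now that the ring is out, does not meet 7.5.6 under either parsing. The result does not turn on grammar.

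**The same finding under Section 8.** If it is an unfavorable, unintended sign that arose in temporal association with the ring, it is an AE. Day 30 lies inside the collection window, and Grade 1 has room for an event without treatment. No passage says which section prevails.

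**The case against.** The strongest reply is that 7.5.6 contains no *only*. It says that findings meeting its conditions will be recorded, which is a sufficient condition and excludes nothing. Section 7.5.1 refers AE matters to Section 8, and Section 8 already counts the finding. This stands. A reader might infer that self-resolving ring injury seen on Day 30 is not counted as an AE, but the documents do not support that. They support only that two sections give different answers.

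Further replies, and what remains of each:

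- **The rule may not reach the speculum examination.** It speaks of a physical examination finding, while pelvic examination has its own row in Table 1.1, its own entry in 7.5.3, its own endpoint in 9.4.2 and its own item in 9.6. This stands as an uncertainty. That the rule applies is inferred from its place directly after the description of the pelvic examination. If it does not apply, pelvic findings have no specific AE rule, which also needs stating.
- **The data are not lost.** Correct. Abnormal findings go into the eCRF, and pelvic findings are tabulated whether or not they are AEs. What can be lost is the grade, the relationship and the entry in the AE table.
- **There are other routes.** Symptoms that a subject reports are AEs under Section 8. Symptom-directed physical examinations are planned at other visits (Table 1.1, footnote c). For early terminators, end-of-study procedures take place at discontinuation (Section 4.1.2), where D can apply. The gap is therefore confined to completers whose finding is seen but not otherwise reported.
- **Divergence between sites is speculative.** The protocol speaks of a single clinical research unit. The remaining risk is inconsistent handling by its staff or at data review.

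A reader might also be tempted to size the effect with the placebo-ring figure in Section 2.3, 8 of 44 subjects (18.2%), which gives 20 × 8/44 = 3.6 of the 20 ring subjects. That figure is for vulvovaginal discomfort, a symptom already reported as an AE. It says nothing about how often an untreated, clinically significant sign is found on examination, so it does not measure this gap.

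**Conclusion.** The point holds as an internal inconsistency of minor severity. Section 7.5.6 is narrower than 7.5.2 and 7.5.5 and conflicts with Section 8 and the Grade 1 definition. For a ring subject who completes, a clinically significant but untreated local finding on Day 30 is an AE under Section 8 and does not meet 7.5.6.

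This rests on three conditions: the 7.5.6 rule is meant to cover pelvic findings, the subject completes treatment, and the investigator judges the finding clinically significant without treating it. The documents give no rate for such findings, so neither the number affected nor the direction of any understatement in a particular table can be quantified. The finding itself would remain visible under the pelvic examination endpoint.

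**What to change.** Make two changes to Section 7.5.6:

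1. Replace the *and* that joins clinical significance to the consequences with *or*, so that clinical significance suffices, as it does once confirmed in 7.5.2 and 7.5.5.
2. State that the rule covers pelvic speculum and visual findings that are new or worse than at screening and are judged clinically significant, whether or not they are treated.

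Keep the clinical significance condition. Recording every new pelvic finding as an AE would create a fresh mismatch with 7.5.2 and 7.5.5. It could also count expected hormonal change as harm, since Section 2.3 describes the irritation in sheep as partly the expected pharmacodynamic response.

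The cost is two sentences in the protocol and a matching line in the eCRF guidance. Only documentation changes; clinical management is untouched. The downside is possibly a few more mild local AEs. They would appear in the ring arms alone, because under 7.5.6 and Table 1.2 the oral arm has no Day 30 pelvic examination, and the report should say so.

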7.5.7 Electrocardiograms

Electrocardiogram assessments will be conducted at screening and Day -1 only for subject inclusion/exclusion purposes.

7.5.8 Appropriateness of Safety Assessments

Safety evaluations selected for this study are typical of those for this subject population and utilize widely accepted measures.

8 ADVERSE EVENTS

An AE is defined as any untoward medical occurrence in a subject administered a pharmaceutical product during the course of a clinical investigation. An AE can therefore be any unfavorable and unintended sign, symptom, or disease temporally associated with the use of a study drug, whether or not thought to be related to the study drug.

Subjects will be monitored throughout the study for AEs, from IVR placement or first oral dose, as applicable, through the follow-up phone call. Adverse events that are identified at the last assessment visit (or the early termination visit) as specified in the protocol must be recorded on the AE eCRF with the status of the AE noted. All events that are ongoing at this time will be recorded as ongoing on the eCRF. All (both serious and nonserious) AEs must be followed until they are resolved or stabilized, or until reasonable attempts to determine resolution of the event are exhausted. The investigator should use his/her discretion in ordering additional tests as necessary to monitor the resolution of such events.

The procedures specified in Section 8.4 are to be followed for reporting SAEs.

8.1 Recording Adverse Events

Adverse events are to be recorded on the AE page of the eCRF. The following information will be recorded:

- Assessment of whether or not the AE is an SAE (Section 8.2.1)
- Assessment of AE intensity (Section 8.2.2)
- Assessment of AE relationship to study drug (Section 8.2.3)
- Action taken - categorized as dose increased, dose not changed, drug interrupted, drug withdrawn, not applicable, or unknown, as applicable
- Outcome - recorded as fatal, not recovered/not resolved, recovered/resolved, recovered/resolved with sequelae, recovering/resolving, or unknown, as applicable

8.2 Assessment of Adverse Events

The investigator will assess each AE for seriousness, intensity, and relationship to study drug.

CONFIDENTIAL

8.2.1 Serious Adverse Events

The investigator is responsible for determining whether an AE meets the definition of an SAE. An SAE is any AE occurring from ICF signing through the follow-up phone call that results in any of the following outcomes:

- Death
- A life-threatening adverse drug experience
- Inpatient hospitalization or prolongation of existing hospitalization
- A persistent or significant disability/incapacity
- A congenital anomaly/birth defect
- An important medical event*

*Important medical events that may not result in death, be life threatening, or require hospitalization may be considered an SAE when, based upon appropriate medical judgment. They may jeopardize the subject and may require medical or surgical intervention to prevent any of the outcomes listed in this definition. Examples of such medical events include allergic bronchospasm requiring intensive treatment in an emergency room or at home, blood dyscrasias or convulsions that do not result in inpatient hospitalization, or the development of drug dependency or drug abuse.

Note: SAEs require immediate reporting to the sponsor and medical monitor. Refer to Section [8.4](#) for details.

8.2.2 Intensity

The intensity of an AE will be graded according to the following definitions:

- Grade 1: Mild; the subject experiences awareness of signs or symptoms but these are easily tolerated or managed without specific treatment.
- Grade 2: Moderate; the subject experiences discomfort enough to cause interference with usual activity, and/or the condition requires specific treatment.
- Grade 3: Severe; the subject is incapacitated with inability to work or do usual activity, and/or the event requires significant treatment measures.
- Grade 4: Disabling or with life threatening consequences, urgent intervention indicated
- Grade 5: Death

CONFIDENTIAL

